7.3 Study Population

All study population summaries will be presented by treatment and overall, as well as by study time period (1A, 2A, 2B) and for study part 2.

7.3.1 Subject Disposition

Subject disposition will be listed for all enrolled subjects. For subjects who are randomized, the subject's study part, gender, age, race, consent date, randomization date, first and last dosing date, reason for treatment discontinuation, off-study date, and reason for going off-study will be listed. For subjects who enroll, but are not treated, the subject's gender, age, race, consent date, and reason for not entering the treatment period will be listed.

Summary tables reflecting the number of subjects enrolled, randomized, and treated, reasons for not entering the treatment period, and number completing the study will be presented by treatment and study time period (1A, 2A, 2B), and for study part 2.

The number of subjects who do not complete treatment and also the number who do not complete the study, both overall and according to reasons for discontinuation, will also be summarized by treatment and study time period (1A, 2A, 2B), and for study part 2..

7.3.2 Demographic and Baseline Characteristics

The following baseline characteristics will be summarized by treatment group for all randomized subjects, overall, as well as by study time period (1A, 2A, 2B), and for study part 2. All baseline presentations will identify subjects with missing measurements.

- Age (descriptive statistics)
- Age category I, in years (< 65, ≥ 65)
- Age category II, in years (< 65, ≥ 65- < 75, ≥ 75)
- Gender (male, female)
- Race (White, Black or African American, Asian, American Indian or Alaska Native, Native Hawaiian or Other pacific islander, Other)
- Ethnicity (Hispanic/Latino, Non Hispanic/Latino) for US subjects
- Geographical Region (North America, Europe, Asia / Pacific)
- Height, Weight, and BMI
- Acute Ischemic Stroke at Entry (Yes/No)
- National Institutes of Health Stroke Score (NIHSS) at Baseline
- High-risk Transient Ischemic Attack at Entry (Yes/No)
- Lacunar Infarct
- Diabetes mellitus (Yes/No)
- Cigarette use (Yes/No)
- Hypercholesterolemia (Yes/No)
- Hypertension (Yes/No)
- BMI Category (<18, 18-25, 25-30, 30-35, >35)

- Vital signs
- Time since onset of symptoms detected to randomization

7.3.3 Medical History

General medical history will be summarized by treatment and study time period (1A, 2A, 2B), and for study part 2.

7.4 Extent of Exposure

7.4.1 Administration of Study Therapy

The number of days on study medication received will be calculated as (date of first dose - date of last dose) + 1. The days on study medication will be summarized for all treated subjects by treatment and study time period (1A, 2A, 2B), and for study part 2 using descriptive statistics as well as categorically as given in the table below.

Table 7.4.1-1: Extent of Exposure Categories for Summarization

Part 1 Exposure Categories	Part 2 Exposure Categories
1 - 7 days	1 - 14 days
8 - 14 days	15 - 28 days
15 - 21 days	28 - 42 days
22 - 28 days	43 - 56 days
> 28 days	57 - 70 days
	71 - 84 days
	> 85 days

A by-subject listing of dosing of study medication and a listing of batch numbers will be also provided.

7.4.2 Study Therapy Compliance

Compliance with the protocol-specified study therapy will be summarized by treatment group for all treated subjects by treatment and study time period (1A, 2A, 2B), and for study part 2.

For randomized study therapy, the case report forms collect the number of doses taken per day. The kits dispensed for study treatment are expected to contain 4 pills per day during Phase A of the study while the high dose arm is closed. During Phase B, once the high-dose arm has opened, the number of pills dispensed to patients who are randomized from that point forward will be 2. Thus, compliance with randomized therapy dosing will be calculated as given below for each container of study therapy:

$$\% \text{ Compliance}_{\text{Randomized Therapy}} = 100 \times \frac{\text{Number of Tablets Taken per Day}}{(\text{Phase A: 4 or Phase B: 2})}$$

Overall compliance will be calculated as the weighted average of the compliance for each container, weighted in proportion to the # of days each container was used.

Acetylsalicylic acid (ASA) is an adjuvant therapy that the protocol requires all subjects receive at a total daily dose that is between 75mg and 162mg. Overall compliance with ASA dosing will be calculated as given below:

$$\% \text{ Compliance}_{ASA} = 100 \times \frac{\text{Number of Days where protocol specified TDD was taken}}{(\text{Last Date Dosed} - \text{First Date Dosed}) + 1}$$

In addition, compliance will also be summarized from the first dose date to the lesser of the last date dosed and 28 days after the first date dosed. The above calculations will be repeated using only data within this time period.

Summaries of compliance will be presented according to the general methods for continuous variables as well as categorically, according to the number and percentage of subjects with compliance in each of the following categories:

- < 80%
- ≥ 80% and ≤ 120%
- >120%

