3.5 Discontinuation of Subjects following any Treatment with Study Drug

During treatment period circumstances may arise which require temporary or permanent discontinuation of investigational product. For guidance related to the temporary discontinuation please refer to [Section 3.4.1](#).

Subjects MUST discontinue investigational product (and non-investigational product at the discretion of the investigator) for any of the following reasons:

- Subject's request to stop study treatment
- Any clinical adverse event (AE), laboratory abnormality or intercurrent illness which, in the opinion of the investigator, indicates that continued participation in the study is not in the best interest of the subject
- Any clinical condition requiring treatment with a prohibited medication for more than 14 days
- Termination of the study by Bristol-Myers Squibb (BMS)
- Loss of ability to freely provide consent through imprisonment or involuntarily incarceration for treatment of either a psychiatric or physical (eg, infectious disease) illness
- Severe non-compliance to protocol, as judged by the investigator and/or Sponsor (BMS)
- Incorrect enrollment (ie, the subject does not meet the required inclusion/exclusion criteria) for the study, as determined after consultation with the sponsor
- Pregnancy
- Moderate or severe renal impairment defined as eGFR < 45 mL/min (see [section 5.3.7.1](#)) for more than 7 days.
- Subjects with an ALT and/or AST > 3× ULN will be scheduled for a follow up visit within 3 days following the receipt of the result. Subjects should be discontinued from study if the initial and repeat laboratory tests meet any of the following criteria:
 - ◆ ALT and/or AST are > 3× ULN and total bilirubin (TB) > 2× ULN

- ◆ ALT and/or AST are $> 5 \times$ ULN for ≥ 14 consecutive days, at any time after initial confirmatory results
- ◆ ALT and/or AST are $\geq 10 \times$ ULN
- Subjects requiring treatment with strong CYP3A4 inhibitors or strong CYP3A4 inducers
- Subjects treated with any intravenous or intra-arterial thrombolysis or with mechanical thrombectomy

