4.5 Selection and Timing of Dose for Each Subject

Study drug may be administered in the clinical facility or self-administered by the subject or their caregiver at home. Caregivers will need to be properly instructed about study medication dosing requirements by the study staff. The same caregiver should assist the subject with their daily dosing.

Double blind study medication (BMS-986141 or matching placebo) will be taken once daily. The first dose of study medication should be taken as soon as possible after randomization. Subsequent doses including on Day 2 of the study should be taken in the morning and before breakfast. The subject must be in a fasted state for at least two (2) hours when taking study medication. Subjects should wait at least one (1) hour before consuming food.

Initially, each daily dose of double blind study medication will consist of 4 tablets. The double blind treatment period will be 28 days for Part 1 of the study and 90 days for Part 2 of the study. Drug supplies that may become available in early 2017 may allow for dosing with 2 tablets per day. Sites will be provided with instructions and guidance on how to implement this change if it is to occur.

Subjects treated in Part 1 of the study MUST be instructed to stop study medication dosing on Day 28, even if visit will not occur on exactly Day 28.

Sparse PK sampling will occur at the Day 28 visit. Subjects will be instructed not to take their study medication dosage on Day 28 prior to coming to the study site.

Additional drug, dosage and mode of administration

All subjects will be dispensed open label ASA at a dose prescribed by the investigator (not less than 75 mg and not to exceed 162 mg per day). It is recommended subjects remain on the same dose of ASA throughout the treatment period.

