6.3 Populations for Analyses

The analyses will use several populations as defined below.

- 1) All Enrolled Subjects: Includes all subjects who signed informed consent.
- 2) All Randomized Subjects / Intent to Treat (ITT) Population: Includes all subjects who were randomized to a treatment, regardless of whether they received study drug or not. This population will be analyzed according to the treatment assigned at randomization.
- 3) All Evaluable Subjects: Includes All Randomized Subjects as above, excluding those subjects' visits where relevant protocol deviations occurred, as defined in [Section 7.2.2](#).
- 4) All Treated Subjects: Includes all subjects who received at least one dose of study medication. This will be the primary population used in safety analyses and will be analyzed according to the treatment assigned at randomization, except in the following cases:
 - If a subject received the same incorrect treatment throughout the study (until either Day 28 or Day 90, or until discontinuation of the study drug), then the subject will be analyzed based on the treatment received.

- If a subject received study drug from more than one treatment group, and none of the administrations were consistent with the assigned randomized treatment group, then the subject will be analyzed based on the first treatment received.
- 5) Pharmacodynamics (PD) Population: A subset of the ITT Population that includes subjects with at least one pharmacodynamic endpoint assessed following the first dose of BMS-986141.
 - 6) Pharmacokinetic (PK) Population: Includes all subjects treated with BMS-986141 who also have at least one post-dose PK sample. The Evaluable PK Population is further defined as a subset of the PK Population including subjects who have adequate PK profiles on Day 1.

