7.2.2 Relevant Protocol Deviations

Relevant deviations from the study protocol will be documented and accounted for in presenting the data summaries, listings and descriptive statistical analyses. Any changes from planned protocol-specified analyses will be defined in the SAP and reported in the CSR. The relevant protocol deviations are described in the table below.

Table 7.2.2-1: List of Relevant Protocol Deviations

Number	RPD Criteria
1	Subject randomized but not dosed
2	Error in treatment assignment (resulting in a subject receiving a treatment other than that assigned by the IVRS) during the first 28-day interval
3	Poor treatment compliance for either BMS-986141 or ASA (compliance less than 80% or more than 120%) during first 28-day interval
4	Randomized subjects with history of atrial fibrillation (AF) other than transient AF related to cardiac surgery at enrollment (per Exclusion Criteria 1a from the protocol)
5	Randomized subjects with unrecognized or misdiagnosed intracranial hemorrhage (ICH) as determined by the central reader based on the baseline study specific MRI (presence of type 1 or 2 parenchymal hematoma)
6	Randomized subjects who took no dose of ASA or dose of ASA not within limits designated by the protocol for ≥ 5 consecutive days in the first 28 days of the treatment period
7	Randomized subjects who took oral anticoagulants or prohibited antiplatelet therapy, other than study medication, for > 2 consecutive days during the first 28days of the treatment period
8	Randomized subjects that were treated with a strong CYP3A4 inhibitor for > 5 days during the first 28 days of the treatment period ^a

a: CYP3A4 inhibitors will be defined in a separate file maintained by the study team and will be classified as weak, moderate, or strong.

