7.5.1.1 Sensitivity Analyses

To assess the robustness of the primary efficacy analysis, additional sensitivity analyses will be carried out using the following approaches:

- Following the same procedure as the primary analysis, considering the All Evaluable Subjects population in place of the All Randomized Subjects population.
- A worst-case analysis that will repeat the primary analysis on the ITT population where any missing information that is consequential to the evaluation of the primary endpoint will be considered as an event.

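### The 28-day compliance measure behind the All Evaluable Subjects set ends at the last dose, so permanent early stoppers score 100% and are kept while a subject taking 22 of 28 daily doses is removed

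*SAP*

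**What the plan says.** SAP 7.5.1.1 plans to repeat the primary dose-response analysis "considering the All Evaluable Subjects population in place of the All Randomized Subjects population". SAP 6.3 forms that set from all randomized subjects, leaving out "visits where relevant protocol deviations occurred, as defined in" Section 7.2.2. Item 3 of Table 7.2.2-1 is "Poor treatment compliance for either BMS-986141 or ASA (compliance less than 80% or more than 120%) during first 28-day interval".

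Item 3 does not cite a formula. SAP 7.4.2 uses the same 80% and 120% limits and is the only place that defines compliance over about 28 days: it runs "from the first dose date to the lesser of the last date dosed and 28 days after the first date dosed". Study-drug compliance is computed per container as tablets taken per day over 4 (Phase A) or 2 (Phase B), then averaged with weights for the days each container was in use.

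On the divisor, SAP 7.4.2 says that once the high-dose arm opens, "the number of pills dispensed to patients who are randomized from that point forward will be 2". Protocol 4.5 gives a different trigger: "Drug supplies that may become available in early 2017 may allow for dosing with 2 tablets per day".

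On CYP3A4, item 8 is "Randomized subjects that were treated with a strong CYP3A4 inhibitor for > 5 days during the first 28 days of the treatment period". Protocol 3.5 lists as one reason for mandatory discontinuation "Subjects requiring treatment with strong CYP3A4 inhibitors or strong CYP3A4 inducers", and exclusion criterion 6g also treats the two classes alike.

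**The concern.** Subjects who stop drug early still reach the analysis. Protocol 3.6 keeps them in follow-up, and the schedules in Protocol Tables 5.1-2 and 5.1-3 ask for their MRI on Day 28. A compliance rule that ignores time after the last dose therefore orders subjects inconsistently. Someone never dosed is removed (item 1), someone dosed once is kept at 100%, and someone dosed on 22 of 28 days is removed.

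At stake is what a reader may conclude when the All Evaluable result agrees with the intent-to-treat result. If the least-exposed treated subjects sit in both sets, agreement says little about whether departures from dosing mattered. The other SAP sensitivity analysis counts missing outcomes as events and does not address exposure. The divisor and the missing inducer term affect the same set in a smaller way.

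**Working it through.** The plan states no figure for this point, so there is none to reproduce. The check applies the SAP 7.4.2 rule literally to worked subjects.

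**Inputs.** Limits 80% and 120% (SAP Table 7.2.2-1, item 3). Window from first dose to the earlier of last dose and 28 days later (SAP 7.4.2). Divisor 4 or 2 tablets (SAP 7.4.2). First 28 days as the reference interval (item 3). A container's days of use are read as running from first to last use.

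**1. Early stopping.** For a subject with full daily dosing up to a permanent stop on day *d*:

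- SAP compliance = *d*/*d* = 100% for every *d*.
- Share of 28 planned days = *d*/28.

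| Dosing pattern | SAP 7.4.2 | Item 3 as written | Share of 28 days | Item 3 with 28-day denominator |
|---|---|---|---|---|
| Stops after Day 1 | 100% | kept | 1/28 = 3.6% | removed |
| Stops after Day 3 | 100% | kept | 3/28 = 10.7% | removed |
| Stops after Day 7 | 100% | kept | 7/28 = 25.0% | removed |
| Stops after Day 14 | 100% | kept | 14/28 = 50.0% | removed |
| Stops after Day 22 | 100% | kept | 22/28 = 78.6% | removed |
| Stops after Day 23 | 100% | kept | 23/28 = 82.1% | kept |
| 22 of 28 days, last dose Day 28 | 22/28 = 78.6% | removed | 78.6% | removed |

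The fifth and last rows have the same number of doses and opposite outcomes under the plan. The window can span 29 calendar days, which is immaterial (28/29 = 96.6%).

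**2. Tablet divisor, if supply and phase change on different dates.**

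- Phase A subject, 2-tablet supply, fully adherent: 2/4 = 50%, removed.
- Phase B subject, 4-tablet supply, fully adherent: 4/2 = 200%, removed.
- Phase B subject, 4-tablet supply, taking half: 2/2 = 100%, kept.

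**3. Inducers.** No item in the table names them. A user who stops study drug, as Protocol 3.5 requires, becomes an early stopper scored at 100%.

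**4. Illustrative size.** The documents give no stopping rate. Assume that a fraction *f* of active-arm subjects stops early and reverts fully to the placebo rate. The retained relative risk reduction is 30% × (1 − *f*): 28.5% at 5%, 27% at 10%, 24% at 20%.

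**The case against.** The strongest reply is that All Evaluable Subjects is a deviation-based set and not one selected on dose received. SAP 7.5.1.1 speaks only of robustness. Stopping for a reason that the protocol allows is not a deviation, and the SAP reports persistence separately, through exposure categories (7.4.1) and reasons for discontinuation (7.3.1). This stands in part: a reader might infer that the analysis was meant for adequately dosed subjects, and the documents do not say so. It does not rescue the rule. Item 3 already removes people for gaps that the protocol permits. A temporary interruption of 14 days, allowed under Protocol 3.4.1, gives (28 − 14)/28 = 50% if dosing resumes and continues to Day 28. And if item 3 was meant to use some other measure, that measure is undefined.

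Four further replies carry weight:

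- Items 6 and 7 can catch stoppers who also drop ASA or take prohibited antithrombotics. The filter is incomplete, not empty.
- The divisor problem is conditional. The SAP expects 4 tablets in Phase A and 2 in Phase B, and nothing shows that the dates differ. A reader might infer that fully dosed subjects will be dropped; the documents support only that they could be.
- Inducer users should be few, since criterion 6g excludes them at entry, and SAP 7.4.4 would list the drugs by class and generic name. The documents give no effect of inducers on exposure, so calling a user who keeps dosing under-dosed is unsupported.
- Protocol 8.4.2.1 has a further sensitivity analysis (treated, with an evaluable Day 28 MRI or an adjudicated stroke). It does not select on exposure after the first dose either.

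The dilution in the illustration affects the intent-to-treat analysis equally, so on this point the Evaluable set is no worse than the primary one. The shift is also small against sampling error. At 348 placebo and 270 subjects on 8 mg, with 14% and 9.8% events, the approximate 95% interval for a 30% relative reduction is −9% to 55%.

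**Conclusion.** The point holds for early stoppers. As written, the 28-day compliance rule keeps treated subjects who stop permanently, however early, unless another deviation removes them, and it excludes some who took far more drug. The divisor is a smaller, conditional weakness. The omission of inducers is a mismatch between protocol and SAP that should be reconciled.

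The reach is one sensitivity analysis. A reader might infer that the primary dose-response result is biased, or that early stopping rises with dose and so blurs the contrast. The documents support neither: the primary analysis is on the intent-to-treat population, and no discontinuation rate is given, overall or by dose. The 24% to 28.5% range rests wholly on the assumed 5% to 20% stopping and on full loss of effect. The conclusion also rests on reading item 3 as using the 7.4.2 measure, which the shared limits and window make the natural reading.

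**What to change.** 1. **SAP 7.4.2, for item 3:** divide tablets taken by tablets due from Day 1 to Day 28. Shorten the window only when the subject was still on drug at the onset of a primary-endpoint stroke or at death. Shortening it at any stroke would select on outcome: a subject who stops after Day 10 and has a stroke on Day 12 would score 10/12 = 83% and stay in as an event, while the same stopper without a stroke would score 10/28 = 36% and be removed. With the restriction, both score 36% and both are removed.
2. **Divisor:** replace the phase-based 4 or 2 with the tablets per day of the container actually dispensed. Full adherence then scores 100% whenever the supply changes.
3. **Table 7.2.2-1, item 8:** reconcile with Protocol 3.5 and criterion 6g by naming strong CYP3A4 inducers beside strong inhibitors. This concerns the analysis set only and implies no change to clinical management.

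The cost is SAP wording and derivation code, settled before unblinding. Container numbers, dosing dates and concomitant medications are already collected. The Evaluable set becomes somewhat smaller. As in any set defined after randomization, some selection remains, so it should stay a sensitivity analysis only.

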7.4.3 Modifications of Study Therapy

The dosage of double blind study medication may not be increased or decreased during the treatment period. Double blind study medication may be interrupted if treatment with prohibited or restricted concomitant therapies is needed as specified in section 3.4.1 of the protocol.

7.4.4 Concomitant Medications

Concomitant medications, defined as medications other than study medications which are taken at any time on-treatment (ie, on or after the first day of study therapy and prior to the last dose of study therapy), will be coded using the WHO Drug Dictionary.

Concomitant medications will be summarized (subjects with any concomitant medication, subjects by medication class and generic term) for all treated subjects. Additionally, a separate, but similar summary of all concomitant medications that are moderate CYP3A4 inhibitors will be created.

7.5 Efficacy

Adjudicated events will be the basis for the primary and secondary analyses, including imaging assessments from the Imaging Adjudication Committee (IAC) and clinical assessments from the CEC. All efficacy analyses will be conducted on the Intent-To-Treat (ITT) population.

7.5.1 Primary Efficacy Analysis

Using the general methods for efficacy analyses described in 17, the observed incidence of the composite of symptomatic ischemic stroke by Day 28 and unrecognized brain infarction assessed

by MRI at Day 28 will be summarized by treatment using the fitted model from the gMCP-Mod procedure. It should be noted that the selected model from gMCP-Mod will actually be a model for the logit of the incidence rate. As a result, the point estimate will be converted and presented on the probability scale by treatment.

In addition, the raw proportion of incidence within each treatment group and its associated 95% Clopper-Pearson CI will be presented. The relative risk reduction between each BMS-986141 arm and placebo and the associated 95% CI will be presented as well. The form of the relative risk reduction between each treatment group and placebo is given below.

$$\frac{Incidence_{PBO} - Incidence_{TRT}}{Incidence_{PBO}} = 1 - \frac{Incidence_{TRT}}{Incidence_{PBO}}$$

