8.4.2 Efficacy Analyses

8.4.2.1 Primary Efficacy Endpoint Analysis

To demonstrate the dose-response relationship between BMS-986141 treatment (including placebo) and primary endpoint, the primary analysis will be based on a Multiple Comparisons and Modeling (MCP-Mod) analysis.^{15,16} This analysis tests for a dose-response relationship, allowing for uncertainty in the dose-response relationship through inclusion of contrasts from two pre-specified candidate models to assess dose-response. If a dose-response relationship exists, then fitted estimates for the incidence of the primary endpoint will be calculated in each of the treatment groups using the selected dose-response model, or using a weighted model-averaging method if significance is detected using both models. Candidate models will include an Emax model and a logistic model, where dose-response will be tested using dose levels of 0 (placebo), 1, 2, and 2.3 (corresponding to 0.8 mg, 4.8 mg, and 8 mg)¹⁷. The parameters used to determine the contrast for testing will include assumed placebo event rate 14% and maximum risk reduction of 4.2%. For the Emax model, the parameters used will be 1.0 for the dose corresponding to half of the maximum effect and 1.0 for a “Hill” parameter that determines the steepness of the model at the dose of half effect. For the logistic model, the initial parameters used will be 1.0 for the dose corresponding to half effect and 0.1 for the parameter that determines the steepness of the curve.

The incidence of the composite of adjudicated symptomatic recurrent ischemic stroke by Day 28 and unrecognized brain infarction at Day 28 will also be summarized by treatment. Point

estimates and 95% CIs for event rates will be presented by treatment, together with point estimates and 95% CIs for the relative risk reduction between each BMS-986141 arm and placebo.

A single categorical variable based on study change points (length of treatment [28 or 90 days] and randomization phase [randomized prior to or after DMC safety interim analysis decision]) will be included as a covariate.

A sensitivity analysis will include subjects who are randomized, treated, and with an evaluable MRI at Day 28, or an adjudicated symptomatic recurrent stroke by Day 28.

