2.2 Treatment Assignment

At the screening visit each subject will be assigned a unique sequential subject number by the Interactive Voice Response System (IVRS). The subject number will consist of 5 digits which are assigned sequentially (00001, 00002, 00003, etc.) by the IVRS. This number will be used for

identification throughout the study and will not be used for any other participant. Screening of subjects with lacunar infarcts will be capped at approximately 20%.

In addition to the two Parts of the study noted above, which are related to treatment duration, the study also consists of two phases, each with a slightly different method of assigning study treatment. In Phase A, subjects will be randomized 1:1:1 using IVRS to one of two doses of BMS-986141 (0.8 mg or 4.8 mg) or placebo. In Phase B, subjects will be randomized 1:1:1:1 via IVRS to one of three doses of BMS-986141 (0.8 mg, 4.8 mg, or 8 mg) or placebo. The transition from Phase A to Phase B of the study will only occur after an Independent Data Monitoring Committee (DMC) has reviewed data from the first 10% of the planned subjects (approximately 132 subjects with 28 days of data). As of the time of the writing of this SAP, the decision to move from Part 1 to Part 2 of the study has been made. Some sites will continue to enroll subjects in to Part 1 of the study until Part 2 can be fully implemented. As a result, there will be no subjects randomized in Phase B during Part 1 of the study.

Randomization schedules will be generated by BMS and kept by the IVRS vendor. All subjects will receive open-label ASA at a dose from 75 to 162 mg per day beginning at a time consistent with local standards of care for patients with AIS or TIA. As mentioned in [section 2.1](#), the planned study dosing duration is 28 days for Part 1 of the study and 90 days for Part 2 of the study.

At all study visits when study drug is dispensed, each subject will be assigned a container number by the IVRS. Container numbers will be assigned non-sequentially and will correspond to the numbers printed on the packages and bottles containing study drug, and will be recorded on the appropriate eCRF. The IVRS will be available 24 hours per day, 7 days a week.

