7.1.2 General Methods for Efficacy Analyses

Generalized Multiple Comparison Modelling (gMCP-Mod)

To demonstrate the dose-response relationship between BMS-986141 treatment (including placebo) and the primary endpoint, the primary analysis will be based on a generalized Multiple Comparisons and Modeling (gMCP-Mod) analysis⁵⁶. This analysis tests for a dose-response relationship, allowing for uncertainty in the dose-response relationship through inclusion of contrasts from multiple pre-specified candidate models to assess dose-response. If a dose-response relationship exists, then fitted estimates for the incidence of the primary endpoint will be calculated in each of the treatment groups using the selected dose-response models.

The gMCP-Mod procedure extends the MCP-Mod methodology to non-continuous endpoints. This is accomplished by decoupling the dose-response model from the expected response through the use of an ANOVA style parameterization of the dose-response parameter. For the binary endpoint used in this study, a logistic regression of the event proportion at each dose level will be used, following adjustment for study time period (1A, 2A, 2B) via the inclusion of an additive covariate. After this first step, the mean parameter estimates from the logistic model and the corresponding covariance matrix, both of which are on the logit scale, will then be used during the rest of the gMCP-Mod procedure. Point estimates from the selected models will be displayed on the proportion scale in all statistical outputs.

Candidate Models and Multiple Testing Procedure

There are two candidate models that will be considered for the primary analysis. These are an Emax model and a logistic model, where dose-response will be tested using dose levels of 0 (placebo), 1, 2, and 2.3 (corresponding to 0.8 mg, 4.8 mg, and 8 mg)⁷.

The MCP-Mod procedure requires certain parameter estimates be pre-specified for the candidate models based on available information in order to derive optimum contrast coefficients for testing the null hypothesis: that a dose-response does not exist in any of the candidate models. It

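### SAP 7.5.1 gives no period adjustment for the supportive 8 mg relative risk reduction; as written, 22% of the planned placebo comparator was randomized before 8 mg opened

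*SAP*

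**What the plan says.** SAP 7.5.1 first reports model-based incidences by dose from gMCP-Mod. It then adds descriptive output: "the raw proportion of incidence within each treatment group and its associated 95% Clopper-Pearson CI will be presented". The next sentence is "The relative risk reduction between each BMS-986141 arm and placebo and the associated 95% CI will be presented as well", followed by a formula equivalent to 1 − Incidence(treatment)/Incidence(placebo). Incidence is not defined in that formula, and no covariate, stratum, concurrent-control restriction or interval method is given.

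Allocation changes during the trial. SAP 2.2 states "In Phase A, subjects will be randomized 1:1:1 using IVRS to one of two doses of BMS-986141 (0.8 mg or 4.8 mg) or placebo" and then "In Phase B, subjects will be randomized 1:1:1:1 via IVRS to one of three doses of BMS-986141". It adds that "there will be no subjects randomized in Phase B during Part 1 of the study", so 8 mg exists only in period 2B.

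Protocol 8.4.2.1 describes event rates and RRRs with 95% intervals. Its next paragraph says that "A single categorical variable based on study change points" (treatment length and randomization phase) enters as a covariate. SAP 7.1.2 uses that variable in the first-step logistic regression of gMCP-Mod, "following adjustment for study time period (1A, 2A, 2B) via the inclusion of an additive covariate". SAP 7.5.2 repeats the primary approach for the secondary endpoints.

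**The concern.** When an arm opens late, control subjects randomized before it opened were never at risk of being assigned to it. If the event rate shifts over time, including them carries the shift into the estimated effect. Here this affects one comparison only: the lower doses share placebo's allocation in every period, and 8 mg does not.

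A shift is plausible. Protocol 3.1 stops randomization of lacunar infarcts once they reach about 20% of the study population, so case mix can change as that cap fills. Protocol 7.1 lets the DMC ask for more experience on placebo and the two lower doses, which would enlarge the non-concurrent share. For the Day 90 endpoints there is also a structural difference. Protocol 3.4.1 prohibits other antiplatelet agents only during treatment, which lasts 28 days in Part 1 and 90 days in Part 2. Day 90 events in Part 1 placebo subjects may therefore differ from those in 2B placebo subjects.

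At stake is the per-dose effect size with an interval that the report shows for the top dose. It could disagree with the period-adjusted model estimate in the same section.

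**Working it through.** **Inputs.** Randomization targets come from SAP Table 5-1 (Protocol Table 8.1-1). The 14% placebo rate, the 30% RRR at 8 mg, and 75% and 90% of that reduction at the lower doses come from SAP section 5. The Phase A placebo rates below are my assumption.

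**1. Reproduce the targets.**
- Placebo: 44 + 34 + 270 = 348.
- 0.8 mg and 4.8 mg: 44 + 33 + 270 = 347 each.
- 8 mg: 0 + 0 + 270 = 270.
- Total: 348 + 347 + 347 + 270 = 1312, as stated. (The last row is labelled 1081 although 4 × 270 = 1080; this has no effect here.)

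**2. Share randomized in Phase A.**
- Placebo: (44 + 34)/348 = 78/348 = 22.4%.
- Each lower dose: 77/347 = 22.2%, balanced with placebo.
- 8 mg: 0/270 = 0%.

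**3. Crude 8 mg RRR under assumed drift.** Phase B placebo is 14%, 8 mg is 0.7 × 14% = 9.8%, and pA is the Phase A placebo rate. Pooled placebo = (78·pA + 270·0.14)/348; crude RRR = 1 − 0.098/pooled.

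| pA | Pooled placebo | Crude RRR (truth 30%) |
|---|---|---|
| 10% | 45.60/348 = 13.10% | 25.2% |
| 12% | 47.16/348 = 13.55% | 27.7% |
| 14% | 48.72/348 = 14.00% | 30.0% |
| 16% | 50.28/348 = 14.45% | 32.2% |
| 18% | 51.84/348 = 14.90% | 34.2% |

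If 8 mg truly has no effect, 1 − 0.14/pooled runs from −6.8% (pA 10%) to +6.0% (pA 18%).

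**4. Does period adjustment remove it?** Trials were simulated at 1240 evaluable subjects, with Phase A rates in all arms scaled by 10/14 or 18/14 (1,000 trials each). The median crude 8 mg RRR was 25.3% and 34.1%. The median from a logistic model with an additive phase term was 29.4% and 29.8%.

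**5. Mantel-Haenszel by period.** For stratum i with n1 subjects on 8 mg, n0 on placebo, N = n1 + n0, and events a (8 mg) and b (placebo), the risk ratio is Σ(a·n0/N) / Σ(b·n1/N). In 1A and 2A, a = 0 and n1 = 0, so both terms vanish. Only 2B contributes, which is 270 against 270.

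**6. Additive logistic model.** This does not drop Phase A placebo. Information on the phase effect is proportional to p(1−p)·nA·nB/(nA+nB): 7.29 for placebo, 5.79 for 0.8 mg and 5.50 for 4.8 mg. Placebo's share is 7.29/18.58 = 0.392. The weight of Phase A placebo in the adjusted placebo estimate is then 0.224 × (1 − 0.392) = 0.136, about 14%, with the drift offset through the lower-dose arms.

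**7. Cost in precision.** Delta method on the log scale, at 14% and 9.8%:
- 348 placebo: √(0.86/48.72 + 0.902/26.46) = √0.05174 = 0.227.
- 270 placebo: √(0.86/37.80 + 0.902/26.46) = √0.05684 = 0.238.
- Ratio 0.238/0.227 = 1.05.

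For an RRR of 30%, the 95% Wald interval goes from (−9%, 55%) to (−12%, 56%). The Wald form is my choice, because the SAP names none.

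**The case against.** **The SAP never says that the RRR is raw.** The word attaches to the per-arm proportions, and the section opens by invoking the general efficacy methods, apparently SAP 7.1.2, which include the period covariate. The first-step logistic regression also yields period-adjusted estimates and a covariance matrix for every arm before any contrast is tested, so an adjusted RRR is available whatever the test shows. This stands in part. Raw is the most natural reading, since the formula follows the raw-proportion sentence and has no period term, but it is not explicit. Two programmers could produce different numbers.

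**A breach of the protocol is not shown.** A reader might infer that the SAP removes a covariate the protocol requires for the RRR. Protocol 8.4.2.1 puts the covariate in a separate paragraph that names no particular analysis. Where the protocol wants the variable in arm-versus-placebo intervals, as for bleeding in 8.4.3, it says so. The SAP is silent rather than in declared conflict.

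**The RRR carries no inference.** It has no hypothesis and no alpha. This stands. A reader might infer that type I error is inflated or the primary result biased. The plan tests nothing on the crude RRR, and the gMCP-Mod test and fitted estimates are built on the period-adjusted step.

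**The drift is assumed.** Also right. Moving 14% to 18% or 10% is a relative shift of 4/14 = 29%, and the resulting 4 to 5 points are small against an interval of −9% to 55%. The planned by-period baseline tables could show a change in case mix, but efficacy is not on the list in SAP 7.1.1.

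**Calling the 8 mg comparison non-randomized would go too far.** Of the 348 planned placebo subjects, 270 are randomized concurrently with 8 mg.

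**Conclusion.** The point holds as a gap in the specification of a supportive estimate. Followed as written, SAP 7.5.1 compares 8 mg subjects from period 2B with all placebo subjects, 22.4% of whom entered before 8 mg opened, and it names no interval method. The effect is confined to the 8 mg RRR and its interval, and to the same output for secondary endpoints.

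The bias is conditional. It is zero if event rates are the same in both phases, and −4.8 to +4.2 points around a true 30% if the Phase A placebo rate is 10% or 18%. That range, the 14% Phase B rate and the 30% effect are assumptions, the last two taken from the design. The 22.4% rests on planned targets, which the table note calls estimates. The correction is worth making because the SAP already defines the period variable and the loss of precision is small.

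**What to change.** In SAP 7.5.1, define each RRR and its 95% CI as one minus a Mantel-Haenszel risk ratio stratified by study time period (1A, 2A, 2B), and name the variance or interval method. The 8 mg contrast then uses concurrent 2B placebo only. Keep the crude RRR as a labelled supportive figure, and say in 7.5.2 that the same rule applies to the secondary endpoints.

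A risk ratio standardised from the additive logistic model of SAP 7.1.2 is an acceptable period-adjusted alternative. If it is chosen, the SAP should say that it does not restrict 8 mg to concurrent placebo and that it relies on a phase effect common to all arms on the logit scale.

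The change costs a sentence or two of SAP text and standard stratified output. The standard error of the 8 mg log risk ratio rises from about 0.227 to 0.238. The 0.8 mg and 4.8 mg results are essentially unaffected, and neither sample size nor the primary test changes.
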